#### 9.6.2 Analysis plan for PROs

The analysis time for PROs endpoints is at about 40 months (24 months of accrual + 12 months of treatment + 1 month follow up after treatment + 3 months of data collection and cleaning) after study activation. Subscale scores for all endpoints will be prorated by multiplying the sum of the subscale by the number of items in the subscale, then dividing by the number of items actually answered: Prorated subscale score = (sum of items cores) \* (number of items in subscale) / (number of items answered). When there are missing data, prorating by subscale in this way is acceptable as long as more than 50% of the items are answered in each subscale. For overall QOL, the FACT-G scale is considered to be an acceptable indicator of patient quality of life as long as overall item response rate is greater than 80%. For the four symptoms, the measurement scales (i.e., PROMIS-Fatigue, FAACT-Additional Concerns subscale, FACIT-Diarrhea) must be completed over 50% of the items (e.g., 4 of 7 items, 6 of 11 items and 7 of 12 items) in order to consider each subscale score valid.

Standard descriptive and graphical analyses will be used initially to examine missing data patterns, and to understand the relationship between variables. The assessment scores for the four symptoms and HRQL will be compared between the two treatment arms at baseline, month 3, month 6, month 12, at the end of protocol treatment and 4-week post-treatment (regardless of the reasons for off treatment), using two independent samples t test (or Wilcoxon rank sum test if the distribution of the score is not symmetric). Change in the four symptoms and HRQL between month 3 visit and the baseline visit will be compared between the two arms using two independent sample t tests. Similar analyses will be conducted for each FACT-G subscales as well. The mean score and proportion of moderate/severe symptoms will be compared between treatment arms for each individual FACT-G item at month 3 using Wilcoxon rank sum test and Fisher exact test, respectively, as an exploratory analysis.

Mixed effect models will be constructed as another exploratory analysis to estimate the time profile of HRQL in the two treatment arms and to evaluate treatment-by-time interactions. Time will be included as a continuous variable if there is a linear trend in HRQL over time or a set of dummy variables if non-linear trend exists for HRQL. Likelihood ratio test will be used for model selection. Adjusted covariates included in the mixed effect models will include patient demographic and disease characteristics, such as age, ECOG PS, disease stage, prior therapy, et al.

As an exploratory analysis, patient-reported outcomes will be correlated with PFS (prognostic value of PROs) in the study patients. Patients will be dichotomized (e.g., by median) and/or categorized into groups (e.g, quantiles) based on their HRQL at baseline and 3-month assessment. Kaplan-Meier method, log rank test and Cox models will be used to compare PFS between patients with good QOL and those with poor QOL in the overall patient population. The predictive value of QOL for benefit from entinostat therapy will be examined via the QOL-by-treatment interaction test in a Cox model for PFS. Landmark method will be used when we correlate QOL at month 3 with PFS, and PFS will be defined as time from landmark time point to disease progression or death for these analyses.

In all analyses, P-values will be two-sided. A level of 2.5% will be considered statistically significant for QOL comparison between two arms. For the four symptoms, a level of 0.625% will be considered statistically significant for comparison between treatment arms. For all other analysis, a level of 5% will be considered statistically significant. No adjustment will be made for multiple comparisons for individual FACT-G items.

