#### 9.7.2 Analysis plan for adherence

The analysis time for adherence endpoint is at about 70 months after study activation (same time as final OS analysis). All patients who receive at least one dose of protocol therapy and have sufficient adherence data will be included in the analysis.

The distribution of the adherence score for each agent will be displayed via box-and-whisker plot. The proportion of high, medium and low adherence to each agent will be calculated along with the binomial exact 95% confidence interval. The proportion of high adherence to entinostat and placebo will be compared between arms A and B using Fisher exact test. The proportion of adherence to exemestane will be compared between treatment arms using Fisher exact test as well. In addition, the adherence score for each cycle will be calculated for each agent and plot by treatment cycle to examine how adherence changes over time. The reasons for non-adherence will be summarized for each agent on each arm. The agreement on adherence level during a treatment period will be examined between the pill counts method and the Medication Adherence Scale method.

As an exploratory analysis, the association between baseline HRQL (categorized as good, fair, poor) and adherence to protocol therapy (categorized as high, medium and low adherence or dichotomized as good or poor) during the whole treatment period will be examined in each treatment arm using Fisher exact test. Multivariable logistic regression analysis will be conducted to identify the baseline factors which can predict high adherence. The covariates will include HRQL and other patient demographics and disease characteristics, such as age at diagnosis, ECOG PS, disease stage, prior therapy, et al.

The association between adherence to protocol therapy during the whole treatment period (categorized as high, medium or low) and HRQL (continuous score) at one-month after treatment discontinuation will be examined using ANOVA test and linear regression analysis, adjusting for HRQL at baseline and other demographic and disease characteristics.

Another exploratory analysis is to examine the association between the occurrence of toxicity in the first two cycles and adherence to entinostat after cycle 2 in patients on arm A.

In all analyses, P-values will be two-sided. A level of 5% will be considered statistically significant. No adjustment will be made for multiple comparisons.

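### The exploratory month-3 QOL-versus-PFS comparison pools both arms with no stratification by treatment, so it is confounded if entinostat affects both HRQL and PFS

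*Combined protocol and SAP*

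**What the plan says.** Section 9.6.2 introduces the analysis thus: "As an exploratory analysis, patient-reported outcomes will be correlated with PFS (prognostic value of PROs) in the study patients". Patients are split at the median or into quantile groups "based on their HRQL at baseline and 3-month assessment". Kaplan-Meier curves, log-rank tests and Cox models are then used to "compare PFS between patients with good QOL and those with poor QOL in the overall patient population". No stratification by arm and no treatment covariate is stated, and the covariates of these Cox models are not listed.

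Treatment enters only in the next sentence, for a different question: "The predictive value of QOL for benefit from entinostat therapy will be examined via the QOL-by-treatment interaction test in a Cox model for PFS". For the later time point the plan adds: "Landmark method will be used when we correlate QOL at month 3 with PFS". The significance rule is: "For all other analysis, a level of 5% will be considered statistically significant".

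Elsewhere the plan works within arm. Section 9.5.2 tests acetylation change against PFS in arm A and repeats the analysis separately in arm B. Section 9.7.2 examines baseline HRQL against adherence in each arm.

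Section 9.7.2 also has a regression of HRQL one month after discontinuation on adherence, which "will be examined using ANOVA test and linear regression analysis, adjusting for HRQL at baseline and other demographic and disease characteristics". Arm is not named there.

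**The concern.** Baseline HRQL cannot depend on treatment, but month-3 HRQL can. If entinostat lowers HRQL and prolongs PFS, the good-QOL group at month 3 is enriched with placebo patients, who progress faster. A pooled comparison then pushes the good-QOL group towards looking worse, which hides a real prognostic effect or creates a small false one in the unexpected direction. If entinostat raises HRQL, the distortion runs the other way and exaggerates the association.

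Either way, the pooled test answers a mixture of two questions: whether QOL is prognostic, and what entinostat does to QOL and PFS. The landmark deals with immortal time; it does not rebalance the arms between the QOL groups. At stake is the interpretation of an exploratory result, not the trial's main conclusions.

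**Working it through.** **Inputs from the plan.** PFS (9.2.1): medians 4.1 and 7.1 months, exponential, hazard ratio 0.58, 360 patients. HRQL at month 3 (9.6.1): a 5-point difference is called clinically meaningful; SD 12; 162 analyzable patients per arm; two-sided 0.025; about 93% power. Treated patients (9.3.3): 171 per arm, 342 in all.

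**Reproducing the plan's figures.** The QOL-PFS analysis has no stated power, so the two inputs are checked instead. HRQL power for 5 points, SD 12 and 162 per arm at two-sided 0.025 is 93.4% (normal) or 93.2% (noncentral t), against about 93% stated. PFS power for 247 events, hazard ratio 0.58 and one-sided 0.001 is 88.3% (Schoenfeld), against 88.5% stated. Both reproduce.

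**Step 1: who reaches the landmark.** The control hazard is ln 2 / 4.1 = 0.169 per month. Progression-free at month 3:
- Arm A: exp(−0.169 × 0.58 × 3) = 74.5%, about 134 of 180.
- Arm B: exp(−0.169 × 3) = 60.2%, about 108 of 180.

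Arm A is then 134/(134 + 108) = 55% of those at risk.

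**Step 2: pooled median split.** Assume normal scores with SD 12 and arm A worse by 5 points. The cut m solves 0.553·Φ((m + 5)/12) + 0.447·Φ(m/12) = 0.5. This puts 43% of arm A and 59% of arm B in the good group.

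**Step 3: spurious hazard ratio with no QOL effect within arms.** Solving the pooled Cox score equation over 12 months after the landmark gives a good/poor hazard ratio of 1.09 with about 187 events. The value is 1.085 to 1.093 for 6 to 36 months. The noncentrality is √187/2 × ln 1.091 = 0.60, so the rejection probability is Φ(−1.96 + 0.60) + Φ(−1.96 − 0.60) ≈ 9%. Varying the inputs:

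| Arm A minus arm B in HRQL | PFS HR | Pooled good/poor HR | Rejection |
|---|---|---|---|
| 0 | 0.58 | 1.00 | 5% |
| −2.5 | 0.58 | 1.05 | 6% |
| −5 | 0.58 | 1.09 | 9% |
| −7.5 | 0.58 | 1.14 | 14% |
| −5 | 0.75 | 1.05 | 6% |
| +5 | 0.58 | 0.92 | 9% |
| any | 1.00 | 1.00 | 5% |

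**Step 4: simulation, pooled against arm-stratified log-rank.** This uses 342 treated patients, a landmark at 12 weeks (about 238 at risk) and follow-up assumed uniform over 12 to 36 months. That follow-up is what 24 months of even accrual plus a further 12 months would give. With no within-arm effect, the 5-point difference gives about 9% pooled rejection and about 5% stratified, with a spurious hazard ratio of 1.08 to 1.09, or 0.92 in the other direction. With a true within-arm hazard ratio of 0.75:

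| Entinostat effect on HRQL | Pooled power | Stratified power |
|---|---|---|
| lowers by 5 | 26% | 50% |
| lowers by 2.5 | 38% | 54% |
| none | 49% | 51% |
| raises by 5 | 72% | 51% |

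Small differences between the stratified figures are simulation error. Power depends on follow-up. With 12 months after the landmark, the rows for lowers by 5, none and raises by 5 become 24/45, 44/46 and 66/46. With complete follow-up they become 32/57, 53/57 and 77/59. The pattern does not change.

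**The case against.** **The plan does not forecast a 5-point HRQL difference.** A reader might infer that it does. In 9.6.1 that figure is a meaningful difference used to compute power; Section 1.5 expects HRQL to be comparable between arms. If that expectation is right, the pooled test is sound. This stands, and it is why the size must be given as a range from nothing upward. It does not remove the point: 9.6.1 takes worse HRQL on arm A as its alternative, and the validity of the QOL-PFS test should not depend on which turns out true.

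**Arm is not ignored altogether.** The interaction model would ordinarily carry a treatment main effect and could yield arm-specific QOL effects, and the unspecified Cox models might include arm. That is fair. But the plan assigns the interaction model to predictive value only, and nothing in it corrects the pooled log-rank tests or Kaplan-Meier curves.

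**Baseline QOL is not confounded.** One might extend the concern to the baseline split. Randomization makes baseline HRQL independent of arm, so the mechanism cannot apply.

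**The logistic adherence model is not confounded either.** Adherence is powered in 9.7.1 to detect 75% against 86% between arms, so a reader might infer that "Multivariable logistic regression analysis will be conducted to identify the baseline factors which can predict high adherence" needs an arm term. The predictors are baseline factors, again independent of arm, so omitting arm does not confound them. Whether that model pools the arms is also not stated. The regression of post-treatment HRQL on adherence is different, because both variables follow treatment. The effect there has not been quantified, and its covariate list is open-ended.

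**The analysis is exploratory.** This stands and limits the importance.

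**Conclusion.** The point holds for the month-3 analysis in 9.6.2, as a minor improvement to an exploratory comparison. Confounding requires entinostat to affect both month-3 HRQL and PFS; if either effect is absent there is no bias. At the design PFS effect, the false-positive rate runs from the nominal 5% (equal HRQL) to about 9% (5 points either way). The larger consequence is for power: a real QOL association can lose about half its power if entinostat lowers HRQL by 5 points, or appear stronger than it is if entinostat raises HRQL.

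These figures assume normal HRQL scores, the same HRQL difference among patients still progression-free at the landmark as overall, constant hazards, and the stated follow-up, none of which the documents fix for this analysis. The documents do not support a claim that the baseline QOL analysis or the logistic adherence model is confounded by arm.

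**What to change.** In 9.6.2, state that the log-rank tests and Cox models relating month-3 QOL to PFS are stratified by treatment arm, and that the month-3 Kaplan-Meier curves are shown by arm. Stratifying the baseline QOL analysis the same way is optional, for consistency and precision only.

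In 9.7.2, if the regression of post-treatment HRQL on adherence pools the arms, include a term for arm. The logistic model of baseline factors needs no change on this ground.

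The cost is a sentence or two of SAP wording. Arm is known for every patient, no data, alpha or sample size changes, and stratifying loses essentially no power when HRQL does not differ (51% against 49% pooled).

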#### 9.7 Adherence to Protocol Therapy

Another secondary objective of the study is to measure adherence to protocol therapy. Patient's adherence to protocol therapy will be quantified using pill count (entinostat/placebo) and diary methods (exemestane). The number of pills a patient has taken will be recorded for every cycle (4 weeks). Patients will be instructed to bring their medication bottles (entinostat/placebo) and diaries (exemestane) with them for clinic visits. Clinic or pharmacy staff will count the number of remaining pills (entinostat/placebo) or pill diary doses taken (exemestane), and will calculate the number of pills taken using a treatment form. As administration of entinostat/placebo is weekly, it will be 0-4 doses per cycle.

Dose reduction (from 5mg to 3mg) is allowed for entinostat/placebo due to toxicity in the trial. If more than two consecutive doses of entinostat/placebo, or > two doses of entinostat/placebo per cycle are omitted due to toxicity, the patient will be permanently discontinued from protocol therapy. For exemestane, it will be administered once daily in each cycle, it will be 0-28 pills per cycle. Exemestane dose reductions are not allowed. If exemestane administration is held for > 7 days due to any reason, patient will be considered permanently off protocol treatment.

The adherence score will be calculated as the proportion of the total number of pills a patient actually took over the whole treatment period divided by the total

number of pills a patient should have taken. The strength of doses will be taken into account and the reduced dose of 3mg will be counted as 0.6 full dose (5mg) in adherence score calculation. The timing of doses will not be considered in the study. Data about adherence to protocol therapy will be collected for exemestane and entinostat /placebo separately for each arm. The adherence score will be calculated for each patient for each agent (exemestane and entinostat /placebo) separately. For the evaluation of each agent, patients will be categorized into 3 groups based on the adherence score. An adherence score of > 85% will be considered as high adherence, and an adherence score of < 65% will be considered as low adherence, and patients with an adherence score of 65%-85% will be considered as medium adherence.

Rev. Add7

The ECOG-ACRIN Medication Adherence Scale Modified from the Morisky Index will be administered to understand the reasons for non-adherence to protocol therapy. There will be one Medication Adherence Scale form for each agent (entinostat /placebo and exemestane) in the study and the Medication Adherence Scale form will be administered at 3, 6, 12 months and at the end of treatment (same time with PROs assessment).

#### 9.7.1 Statistical consideration for adherence

The primary analyses for this adherence study will be conducted in patients on arm A who have data about adherence to entinostat. All 300 patients on arm A will be eligible for the analysis. It is expected that about 80% (240) of the 300 patients on arm A will have sufficient data for evaluation of adherence to entinostat therapy and will be included in the analysis. With 240 analyzable patients on the arm A, the binomial exact 95% confidence interval for high adherence rate (defined by adherence score > 85%) to entinostat would be no wider than 0.13. Comparing adherence to entinostat and placebo, there is 84% power to detect a difference in high adherence rate of 75% vs. 86% between arms A and B, assuming a one-sided type I error rate of 2.5%, based on the Fisher's exact test.

#### 9.7.2 Analysis plan for adherence

The analysis time for adherence endpoint is at about 70 months after study activation (same time as final OS analysis). All patients who receive at least one dose of protocol therapy and have sufficient adherence data will be included in the analysis.

The distribution of the adherence score for each agent will be displayed via box-and-whisker plot. The proportion of high, medium and low adherence to each agent will be calculated along with the binomial exact 95% confidence interval. The proportion of high adherence to entinostat and placebo will be compared between arms A and B using Fisher exact test. The proportion of adherence to exemestane will be compared between treatment arms using Fisher exact test as well. In addition, the adherence score for each cycle will be calculated for each agent and plot by treatment cycle to examine how adherence changes over time. The reasons for non-adherence will be summarized for each agent on each arm. The agreement on adherence level during a treatment period will be examined between the pill counts method and the Medication Adherence Scale method.

As an exploratory analysis, the association between baseline HRQL (categorized as good, fair, poor) and adherence to protocol therapy (categorized as high, medium and low adherence or dichotomized as good or poor) during the whole treatment period will be examined in each treatment arm using Fisher exact test. Multivariable logistic regression analysis will be conducted to identify the baseline factors which can predict high adherence. The covariates will include HRQL and other patient demographics and disease characteristics, such as age at diagnosis, ECOG PS, disease stage, prior therapy, et al.

The association between adherence to protocol therapy during the whole treatment period (categorized as high, medium or low) and HRQL (continuous score) at one-month after treatment discontinuation will be examined using ANOVA test and linear regression analysis, adjusting for HRQL at baseline and other demographic and disease characteristics.

Another exploratory analysis is to examine the association between the occurrence of toxicity in the first two cycles and adherence to entinostat after cycle 2 in patients on arm A.

In all analyses, P-values will be two-sided. A level of 5% will be considered statistically significant. No adjustment will be made for multiple comparisons.

9.8 Gender and Ethnicity

Male breast cancer accounts for approximately 1% of all breast cancers. Meanwhile, some elderly male patients may not be eligible or consider trials. We could anticipate that about 5 male patients with HR-positive, HER2-negative metastatic breast cancer could enroll out of a sample size of 600, and all of them are expected to be non-Hispanic White patients. For the 600 patients, based on previous data from SWOG S0226 and ECOG E2100 studies, the anticipated accrual in subgroups defined by gender and race is:

Ethnic Category	Gender		
	Females	Males	Total
Hispanic or Latino	44	0	44
Not Hispanic or Latino	551	5	556
Ethnic Category: Total of all subjects	595	5	600

Racial Category			
American Indian or Alaskan Native	0	0	0
Asian	11	0	11
Black or African American	51	0	51
Native Hawaiian or other Pacific Islander	0	0	0
White	533	5	538
Racial Category: Total of all subjects	595	5	600

The accrual targets in individual cells are not large enough for definitive subgroup analyses. Therefore, overall accrual to the study will not be extended to meet individual subgroup accrual targets.

9.9 Study Monitoring

This study will be monitored by the ECOG-ACRIN Data Safety Monitoring Committee (DSMC). The DSMC meets twice each year. For each meeting, all monitored studies are reviewed for safety and progress toward completion. When appropriate, the DSMC will also review interim analyses of outcome data. Copies of the toxicity reports prepared for the DSMC meetings are included in the study reports prepared for the ECOG-ACRIN group meeting (except that for double blind studies, the DSMC may review unblinded toxicity data, while only pooled or blinded data will be made public). These group meeting reports are made available to the local investigators, who may provide them to their IRBs. Only the study statistician and the DSMC members will have access to interim analyses of outcome data. Prior to completion of this study, any use of outcome data will require approval of the DSMC. Any DSMC recommendations for changes to this study will be circulated to the local investigators in the form of addenda to this protocol document. A complete copy of the ECOG-ACRIN DSMC Policy can be obtained from the ECOG-ACRIN Operations Center.

## 10. Imaging Study

ECOG-ACRIN plans to bank standard practice and protocol-defined imaging studies at the central ACR Imaging Core Laboratory for all 600 enrolled participants. An independent imaging review conducted by the ACR's Image Metrix will centrally evaluate imaging (only for the first-360-enrolled subjects) in relation to therapeutic response, PFS, OS, differences among therapeutic arms, and histologic biology. The independent review will be performed after quality assurance and according to standard operating procedures of the ACR Imaging Core Laboratory. For the ECOG-ACRIN E2112 trial, we plan to evaluate specific clinical data elements to associate images with treatment milestones. In the future, the de-identified image bank may be used for additional research, such as retrospective reviews of disease or software validation. Patient identifiers will never be included in future research and no patients will be named in publications related to future research.

